8.1 Electronic case reporting form

The e-CRF has been approved by the SC. It is identical for each site and is provided in German language. Data will also be collected about the site itself (e.g. type of institution and other administrative data), and basic, pooled details about its patients in focus to allow for control of selection bias.

8.2 Personal data and data protection

All data obtained in the context of this observational clinical study are subject to data protection according to EU GDPR. This applies to patients' data as well as to investigators' personal data which may be included in any database of the sponsor or the CRO. Data protection processes and responsibilities according to EU GDPR are defined in agreements on joined control of data between study sites and the sponsor as well as in an agreement of data processing between the sponsor and the CRO.

The storage of data for statistical assessment shall likewise be performed only under the patient's study number. Only authorised staff members in each site can assign identifiers to personal data. If personal data are stored and processed, requirements for data protection will be followed. The study database is centrally stored on redundant servers in Germany provided by the e-CRF system vendor and under the control of the CRO.

All recorded data will be pseudonymised for storage in the central database during the course of the study. As the decoding information is held only by the treating study sites, nobody else will know the identity of the participating patients. After the end of the project, the data will be deleted from the vendor's servers and transferred to the sponsor where it will be stored according to regulatory requirements and sponsor's SOPs.

Data will only be collected and processed to reach the goals of the study. Personal data of the patient are demographic data (e.g. height, weight, data on comorbidities, data on current therapy), SAEs and therapy data. Data will be transferred to the CRO (database management, data cleaning, data analysis), to sponsor's subsidiaries within the EU and to the scientific SC.

The patient will be informed about the study and her/his rights in terms of data usage, data storage, correction of data and deletion of stored data.

8.3 Completion of Case Report Forms

All medical data within this study will be recorded directly in the e-CRF without the use of paper CRF. The investigator must ensure the accuracy, completeness, legibility and timeliness of data reported in the e-CRF and of all required clinical reports (e. g. in case of SAEs). Any change or correction to the data in the e-CRF must be explained as a prerequisite of the e-CRF system. Any change or correction to an e-CRF item will automatically be tracked (audit trail), recording the person logged-in as well as the time stamp of the change and the reason for change. The e-CRF system will not accept changes without given reason. The history of changes to a single item including original entries is always visible to the responsible local research team and to the CRO.

Data reported in the e-CRF that are derived from source documents should be consistent with the source documents or existing discrepancies should be explained. Upon entry into the e-CRF the data will be automatically stored in the central study database in pseudonymised form.

8.3.1 Data documented by study sites

Data will be derived from clinical routine care records and findings, observations or other sources (e.g. hospital records, clinical and office charts, electronic patient records, laboratory notes, recorded data from automated devices, patient files, laboratories and medico technical departments). In cases where data are collected while speaking to the patient, the e-CRF is the source document (if the patient's answer is documented there without prior documentation on paper).

SAEs during FU will be assessed by the treating investigator.

8.3.2 Quality control

Quality control is defined as the operational techniques and activities undertaken within the quality assurance system to verify that the requirements for quality of the study-related activities have been fulfilled. Quality control should be applied to each stage of data handling to ensure that all data are reliable and have been processed correctly.

Quality assurance is defined as the planned and systematic actions that are established to ensure that the study is performed, and the data generated, documented (recorded) and reported, in compliance with GCP according to ISO 14155:2020 and applicable regulatory requirements.

Source Data

Source data are defined as all information obtained in clinical routine care and stored in original records and certified copies of original records of clinical findings, observations or other activities in a clinical study necessary for the reconstruction and evaluation of the study. Source data are contained in source documents (original records or certified copies).

Source Documents

Source documents are defined as original documents, data and records in clinical routine care (e.g. hospital records, clinical and office charts, laboratory notes, memoranda or evaluation check lists, pharmacy dispensing records, recorded data from automated instruments, copies or manuscripts certified after verification as being accurate copies, microfiches, photographic negatives, microfilm or magnetic media, x- rays, patient files, records kept at pharmacy, at the laboratories and at medico technical departments).

Access to Source Data/Document

The investigator will permit, and participating patients will consent for, study-related monitoring, audits, EC review and regulatory inspections, providing direct access to primary patient data (i.e. source data) that support data in the e-CRFs, i.e. general practice charts, hospital notes, appointment books, original laboratory records, etc. Because this is a patient confidentiality issue, access to such data must form part of the Informed Consent Form to be signed by the patient.

Direct Access

Direct access is defined as the permission to examine, analyse, verify and reproduce any records and reports that are important to the evaluation of a clinical study. No identifiable patient data can be released from a site. Any party (e.g. domestic and foreign regulatory authorities, the sponsor and/or authorised representatives of the sponsor such as monitors and auditors) with direct access should take all reasonable precautions within the constraints of the applicable regulatory requirements to maintain the confidentiality of patient identities and sponsor proprietary information.

Audits

An audit is a systematic and independent review of study-related activities and documents to determine whether the validated study-related activities were conducted and the data were recorded, analysed and accurately reported according to the protocol, designated standard operating procedures (SOP), GCP according to ISO 14155:2020 and applicable regulatory requirements. An independent audit at the site may take place at any time during or after the study.

9. Amendments to the study protocol

Amendments to study protocol will be sent to each corresponding EC. In case of substantial amendments to protocol the vote of the responsible EC is a prerequisite before coming into force for corresponding study sites. In case of non-substantial amendments to protocol modifications will be implemented as soon as the sponsor and the SC signed the document.

Regulatory bodies are not involved in this non-interventional, observational study. Thus, amendments to protocol will not be submitted to them.

10. Deviations from study protocol

Protocol deviations are any unapproved changes, deviations or departures from study design or procedures of a research project that are under the investigator's control and that have not been reviewed and approved by the SC.

This clinical study is purely observational. All procedures and therapies are performed as routine clinical care based on individual decisions by the treating physician and are not defined in the study protocol. This includes timing of procedures and follow-up visits as well as measures available for reporting which are defined as recommendations in the study protocol. Deviations from study protocol might therefore primarily occur for in-and exclusion criteria.

11. Device accountability

No investigational devices are used, thus, device accountability is not applicable.

12. Statements of compliance

This clinical study is purely observational. All therapies used are decided individually by the treating physician and are not pre-defined by the study protocol. All therapies used within this study have to be in line with their marketing authorisation, i.e. IFU.

Participation in this study does not pose additional risks or benefits compared to routine clinical practice because only data created within routine clinical care will be documented in this observational study, no studyspecific interventions will be performed. All therapeutic decisions and procedures should be in accordance with routine clinical care following applicable medical, ethical and regulatory standards, e.g. ICH-GCP according to ISO 14155:2020.

No study-specific insurance is provided for patients who agree to the use of their data within this study.

Before initiating the study in a study site, a positive vote of the corresponding EC will be obtained.

This clinical study is industry funded and solely financed by the sponsor. The costs necessary to perform the study, i.e. to cover the time spent by site staff for documentation work, will be agreed upon with each investigator and will be documented in a separate financial agreement which will be signed by the site and the CRO on behalf of the sponsor, prior to the study commencing.

13. Informed consent process

All clinical data needed to evaluate the potential eligibility of a patient before study inclusion are to be performed during routine clinical care and are therefore not considered to be part of study related procedures.

A signed, EC approved informed consent form for transfer, processing and use of personal medical data, written in accordance with applicable data privacy regulations, will be obtained from every patient prior to any transfer of personal data to the e-CRF. The patient will be given sufficient time to consider the implications of consenting for transfer, processing and use of personal medical data before deciding whether to agree.

Patients undergoing the procedures of interest in this study will often be in a clinical situation requiring immediate therapy without any delay. In addition, it is expected that potential study patients might not be able to give informed consent on the use of their personal data at the time of physician's decision on the primary intervention procedure of interest. Since this clinical study is purely observational, all therapies used are decided individually by the treating physician in routine clinical care in line with medical guidelines and the IFUs of the devices used but not pre-defined in the study protocol. Thus, informed consent for use of personal data will be given subsequent to the primary intervention procedure of interest but before any data transfer to the e-CRF.

Should there be any modifications to the protocol, such that this would directly affect the patient's consent for transfer, processing and use of their personal medical data in the study, an addendum to the informed consent form specifying the modification must be compiled and the active patients must agree to sign this addendum indicating that they also agree to the modifications within the study.

A signed copy of the patient's informed consent form must be maintained in the study file on site, a copy of the signed informed consent form must be provided to the study patient. The patient's permanent medical records should indicate the patient's study participation.

14. Adverse events, adverse device effects and device deficiencies

SAEs will be documented following ISO 14155:2020 and reported in accordance with applicable national standards. Since the study is observational, all therapies and procedures represent routine clinical care in line with applicable medical guidelines, market authorisations and corresponding IFUs. Since no risks or benefits compared to routine clinical care will be added, the rate of non-serious AEs will be identical to routine clinical care. Thus, non-serious AEs will not be documented within this study but AEs of special interest (AEoSI), only (refer to section 14.1).

14.1 Definitions

Adverse Event (AE):

Is any untoward medical occurrence, unintended disease or injury, or untoward clinical signs (including abnormal laboratory findings) in subjects, users or other persons, in the context of a clinical investigation, whether or not related to the investigational medical device. This definition includes events that are anticipated as well as unanticipated events and those occurring in the context of a clinical investigation related to the investigational device, the comparator or the procedures involved. For users or other persons, this definition is restricted to events related to investigational medical devices. A newly diagnosed concomitant disease is also considered an AE.

AE of special interest (AEoSI)

Potential complication of index therapy:

- latrogenic injury of the mucosa;
- Any bleeding, appearance of fistula or abscess, pneumonia, peritonitis, or mediastinitis as a symptom of the treatment;
- Occurrence of stricture / stenosis during the follow-up.

An independent CEC will review AEoSIs based on coded (pseudonymized) copies of corresponding medical files to assess if they fulfil criteria for

Serious Adverse Event (SAE):

A **SAE** is any untoward medical occurrence that

- led to death,
- Ied to serious deterioration in the health of the subject, that either resulted in
 - > a life-threatening illness or injury, or
 - > a permanent impairment of a body structure or a body function, or
 - > hospitalisation or prolongation of patient hospitalisation, or
 - medical or surgical intervention to prevent life-threatening illness or injury or permanent impairment to a body structure or a body function,
 - > a chronic disease,
- Ied to foetal distress, foetal death or a congenital abnormality or birth defect.

More than one of the above criteria can be applicable to each event.

These characteristics/consequences have to be considered at the time of the event. For example, regarding a life-threatening event, this refers to an event in which the subject was at risk of death at the time of the event. It does not refer to an event which hypothetically might have caused death if it were more severe.

NOTE:

- The index treatment itself,
- a planned hospital overnight stay in follow-up for review of index defect,
- an elective hospitalisation (e.g. surgery) verifiably planned before signing consent
- overnight survey visits (e.g. sleep lab)

are not considered as SAEs if no additional medical events occur which fulfil criteria of a SAE.

An independent CEC will review SAEs (and AEoSIs) based on coded (pseudonymized) copies of corresponding medical files to assess if they fulfil criteria for

- defect treatment complication or
- being related to defect treatment.

Life-threatening

The definition of a SAE refers to an event in which the patient was at risk of death at the time of the event. It does not refer to an event which hypothetically might have caused death if it was more severe.

Hospitalisation

- Hospitalisation within this protocol is defined as inpatient care for more than one calendar day (overnight stay) for any cause. Overnight survey visits (e.g. sleep lab) are not considered "hospitalisation".
- Hospitalisation for therapy of index defect follows within this protocol the definition in 6.3.1.

The investigator will document in the e-CRF for each hospitalisation if he classifies it as "for therapy of index defect".

Because hospitalisation decisions might be subject to local practices, social considerations, bed availability, and so on, hospitalisations for SAEs will be reviewed by an independent CEC based on coded (pseudonymized) copies of corresponding medical files to assess the reason and appropriateness of each hospitalisation, i.e. whether it is "for therapy of index defect".

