5.4 Risks and anticipated adverse device effects that are to be assessed

The investigational device is a marketed, CE-certified product, which will be used within its intendent purpose. Rate of defect treatment complications (during index defect treatment and in follow-up treatments) and rate of SAEs related to defect treatment will be assessed. The term "defect treatment related" represents not only device-related but in total procedure-related AEs of special interest and SAEs. Non-serious AEs which are not classified as "of special interest" will not be assessed.

6. Design of the clinical study

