6.1.3 Endpoints of the study

6.1.3.1 Primary endpoint

Time period in days from index use of Suprasorb[®] CNP endo to release for oral food intake (in upper GI tract use) or endoscopic release for stoma relocation (in lower GI tract use).

In case of lower GI tract use and no stoma present, time period to release for oral food intake is the relevant endpoint.

6.1.3.2 Secondary endpoints

- 1. Number of SAEs related to defect treatment within total observation period.
- 2. Number of nights in hospital for therapy of index defect.
- 3. Number of nights at the ICU during hospital stay for therapy of index defect.

Nights at an intermediate care unit (IMC) will not count for this secondary endpoint.

SAEs will be adjudicated by an independent Clinical Event Committee (CEC) according to standard definitions. Wherever reasonable, endpoints will be normalised to one year of follow-up to adapt results to varying follow-up periods.

"Index defect" describes for each study patient the defect(s) which lead to the clinical indication of treatment with Suprasorb[®] CNP endo system according to IFU and medical guidelines as defined in 6.3.1.

"Index therapy" describes for each study patient the first use of Suprasorb[®] CNP endo for therapy of the index defect.

6.1.4 Methods and timing for assessing, recording, and analysing variables

Only data which can be obtained from routine clinical care files of the patients will be recorded. Data of routine clinical care visit after study enrolment will be reported in the e-CRF. Data will be derived from clinical records and findings, radiological assessments, observations or other sources (e.g. hospital records, clinical and office charts, electronic patient records, laboratory notes).

Within this observational study timing of measures and clinical data to be reported are determined by routine clinical care in line with applicable medical guidelines and local policies. The study protocol just defines some procedural recommendations.

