14.3.2 Definition of Causality

The sponsor and the investigators will use the following definitions to assess the relationship of SAEs to the index therapy (devices used and procedure itself).

Not related

Relationship to index therapy can be excluded when:

- the event has no temporal relationship with the use of the devices or the procedures;
- the SAE does not follow a known response pattern to the index therapy (if the response pattern is previously known) and is biologically implausible;
- the discontinuation of the index therapy or the reduction of the level of activation/exposure when clinically feasible - and reintroduction of its use (or increase of the level of activation/exposure), do not impact on the SAE;
- the event involves a body-site or an organ that cannot be affected by the index therapy;
- the SAE can be attributed to another cause (e.g. an underlying or concurrent illness/ clinical condition, an effect of other devices, drugs, treatments or other risk factors).

In order to establish the non-relatedness, not all the criteria listed above might be met at the same time, depending on the type of device/procedures and the SAE.

Possible

The relationship with the index therapy is weak but cannot be ruled out completely. Alternative causes are also possible (e.g. an underlying or concurrent illness/ clinical condition or/and an effect of other devices, drugs or treatments). Cases where relatedness cannot be assessed, or no information has been obtained should also be classified as possible.

Probable

The relationship with the index therapy seems relevant and/or the event cannot be reasonably explained by another cause.

Causal relationship

The SAE is associated with the index therapy beyond reasonable doubt when:

- the event is a known side effect of the index therapy or of similar devices and procedures;
- the event has a temporal relationship with the index therapy;
- the event involves a body-site or organ that
 - the index therapy is applied to;
 - the index therapy has an effect on;
- the SAE follows a known response pattern to the index therapy (if the response pattern is previously known);
- the discontinuation of the index therapy (or reduction of the level of activation/exposure) and reintroduction
 of its use (or increase of the level of activation/exposure), impact on the SAE (when clinically feasible);

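### Adverse events of special interest are tied to the first device use and partly to the site's own attribution, so non-serious complications of later sponge changes can go unrecorded although section 5.4 promises their rate

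*Protocol*

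**What the plan says.** Section 6.1.3 states that index therapy "describes for each study patient the first use of Suprasorb" CNP endo for the index defect. Section 14.1 then heads the AEoSI list "Potential complication of index therapy". The list has three entries:

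- iatrogenic mucosal injury;
- "Any bleeding, appearance of fistula or abscess, pneumonia, peritonitis, or mediastinitis as a symptom of the treatment";
- "Occurrence of stricture / stenosis during the follow-up".

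Section 14.3.2 has the sponsor and the investigators "assess the relationship of SAEs to the index therapy (devices used and procedure itself").

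Other sections name a wider exposure. Section 5.4 says: "Rate of defect treatment complications (during index defect treatment and in follow-up treatments) and rate of SAEs related to defect treatment will be assessed". Sections 1.2 and 14.1 have the CEC decide whether SAEs and AEoSIs are complications of, or related to, *defect treatment*. Secondary endpoint 1 counts SAEs related to defect treatment.

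On capture, 14.3 requires every SAE after the start of index treatment, related or not. Sections 5.4 and 14 exclude non-serious events unless they are AEoSIs.

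**The concern.** Endoscopic vacuum therapy is a series of placements, changes and removals. If the capture definition covers the first use only, while the stated safety target covers the whole course, a non-serious bleed or mucosal tear at a later sponge change meets no reporting definition and is not documented.

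The second list entry adds a separate filter. The site must decide that the event stems from treatment before reporting it, although deciding relatedness is the CEC's task. Section 4 says these patients are at risk of mediastinitis and peritonitis from their underlying condition, so sites may well attribute such events differently.

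At stake is the complication rate in 5.4, and with it the stated aim in 5.2 of detecting unexpected adverse events. A later analysis plan cannot recover events that were never entered.

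**Working it through.** The plan states no figure to reproduce. The check sets the sections side by side.

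**1. Which exposure does each section use?**

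| Section | Function | Exposure named |
|---|---|---|
| 6.1.3 | definition of index therapy | first device use |
| 14.1, AEoSI heading | capture of non-serious events | index therapy |
| 14.1, second AEoSI entry | capture of non-serious events | the treatment, with attribution required |
| 14.3.2 | causality grading of SAEs | index therapy |
| 5.4 | safety target | defect treatment, including follow-up treatments |
| 1.2 and 14.1 | CEC criterion | defect treatment |
| 6.1.3, secondary endpoint 1 | safety endpoint | defect treatment |

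Capture and grading use the narrower term. Target, adjudication and endpoint use the wider one.

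**2. What happens to a serious complication of a later change?** Section 14.3 requires it to be collected whatever its relationship, and 1.2 and 14.1 send it to the CEC. The CEC judges it against defect treatment. Nothing is lost. What remains is that the investigator's grade and the CEC's judgement refer to differently named exposures.

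**3. What happens to a non-serious complication of a later change?** Under the heading in 14.1 and the definition in 6.1.3 it is not an AEoSI. Under 5.4 and 14 it is then not documented. Two other places pull the opposite way. Section 14.2 says that adverse events related to the product will be recorded and reported, and 6.4.5 lists adverse device effects among the events to document. The text therefore gives a site two answers.

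**4. What happens to a non-serious event the site does not attribute to treatment?** For the six types in the second entry it is not an AEoSI, at the first use or at any later one. This filter does not depend on how index therapy is read.

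**5. Does a stricture found during the index stay count?** The third entry needs it to occur during follow-up. Section 6.3.6 counts follow-up from enrolment, which can fall within the stay. Section 6.4.5 counts it from discharge. The answer is ambiguous.

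**6. How much of the treatment course follows the first use?** Section 3.2 cites a median of 3 procedures in a 55-patient upper GI series and a median of 12.5 sessions in a 14-patient colorectal series. Share after the first use = (n − 1)/n:

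- upper GI: (3 − 1)/3 = 67%;
- colorectal: (12.5 − 1)/12.5 = 92%.

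These are shares of procedures computed from medians. They show how much of the course lies outside the literal definition. They are not shares of complications missed.

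**The case against.** The strongest reply is that the first-use reading is literal and probably not what was meant. The scale in 14.3.2 speaks of discontinuing and reintroducing index therapy, which fits a course of treatment better than a single placement. The index-treatment record in 6.4.4 covers the number of changes, the intervals between them, the total length of therapy and findings such as migration or erosion. Section 14.2 and the adverse device effect entries in 6.4.5 suggest that device-related events at any change were meant to be recorded. The AEoSI heading says only *potential* complication, and explicit attribution appears in one list entry of three.

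This stands as evidence of intent, and it limits the claim. It does not remove the conflict. Section 6.1.3 gives an explicit definition, and 5.4 and 14 explicitly exclude other non-serious events. About 10 sites, without routine onsite monitoring (6.5), need one reading.

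A reader might also infer that serious complications can be dropped before the CEC sees them, or that the causality scale screens events out. The documents do not support this. All SAEs are collected, the scale grades events already reported, and it assigns cases that cannot be assessed to *possible*.

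A further objection is that reporting mediastinitis or peritonitis whatever the cause would mix the disease with its complications. That is fair, and the fix below meets it by recording conditions already present at first use as baseline.

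**Conclusion.** The point holds for non-serious events. The protocol's capture definition is narrower than the rate it says it will assess, and for six event types capture also rests on the site's own attribution. The non-serious part of the 5.4 complication rate may be biased downwards. The size cannot be derived from the documents, because it depends on how sites read the term and on when complications occur.

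It would be wrong to read 67% to 92% as the fraction of complications missed. In the 32-patient vacuum-therapy group described in 3.2, one bleed followed sponge removal and one mucosal tear occurred during it, but the text does not say at which removal. Nor does it follow that the 5.4 rate cannot be produced at all, since its serious part is captured in full.

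For SAEs, and so for secondary endpoint 1, the defect is limited to the mismatch of terms between 14.3.2 and the CEC criterion. Whether a stricture in the index stay counts is unclear rather than excluded. The conclusion assumes that sites follow the written definition. If all sites already read index therapy as the whole course, only the attribution filter and the stricture ambiguity remain.

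**What to change.** - In 14.1, 14.3 and 14.3.2, replace *index therapy* and *index treatment* by *defect treatment*, defined as any application, change or removal of the device for the index defect.
- Have sites report the listed AEoSI types by occurrence, when they are new or worsening, from first device use to the end of observation. Include stricture or stenosis in the index stay.
- Record conditions already present at first use as baseline.
- Remove the attribution condition from the second list entry and leave relatedness to the CEC.
- Align 5.4 and 14 with 14.2 and 6.4.5, so that the rule for non-serious device-related events is the same throughout.

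The cost is a wording change, an adjusted AEoSI form in the e-CRF, and some additional non-serious events to document and send to the existing CEC. Patient care is not touched.
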